4.0 STUDY DESIGN

4.1 Overall Design

RPL554-CO-302 is a multicenter, randomized, double blind, parallel group, placebo controlled study to determine the efficacy and safety of ensifentrine 3 mg twice daily (BID) for 24 weeks administered via nebulizer vs. placebo in patients 40 to 80 years of age with moderate to severe COPD (FEV₁ 30% – 70% of predicted, FEV₁/forced vital capacity (FVC) ratio <0.7, with documented COPD symptoms).

Up to 50% of patients recruited will be using stable background maintenance as *either* long-acting muscarinic antagonist (LAMA) *or* long-acting β 2 agonist (LABA) maintenance therapy for 24 weeks and all patients will be provided with rescue albuterol/salbutamol for use as needed during the study. Up to 20% of patients are allowed to take inhaled corticosteroids during the study under certain provisions (see Sections 6.7.2 and 6.7.3). Washout of patients on stable background maintenance LAMA or LABA monotherapy for the sole purpose of study eligibility is not recommended.

Randomization will be stratified by two different factors: stable background maintenance LAMA or LABA therapy use (yes or no) and cigarette smoking (current or former). Patients will be randomized 5:3 to receive ensifentrine (3 mg):placebo for 24 weeks. Patients in the background maintenance LAMA or LABA therapy stratum must withhold Twice-Daily maintenance LAMA or LABA (or LAMA/ICS or LABA/ICS) for 24 hours and Once-Daily maintenance LAMA or LABA (or LAMA/ICS or LABA/ICS) for 48 hours prior to initiation of any spirometry. All patients must withhold short acting bronchodilator (SABA) rescue medication for at least 4 hours prior to initiation of any spirometry.

All sites will use standardized spirometry and ECG equipment provided by a central vendor and all spirometry and ECGs will be over-read by the blinded central vendor.

Patients will be screened for eligibility before entering a 28-day run-in period to ensure a stable background maintenance LAMA or LABA bronchodilator medication regimen and to collect baseline information on symptoms and rescue medication use. Permitted rescue and background medications and the condition of their use during the study are described in Section 6.7.2. Prohibited medications and the prohibited time intervals prior to Screening are described in Section 6.7.3

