9.2 Sample Size Determination

Approximately 800 patients will be randomized. The standard deviation for the change in FEV₁ AUC_{0-12h} is estimated to be 250 mL. With a 2-sided test at a 5% significance level and 500 vs. 300 evaluable patients in the two groups, there will be an 90% power to detect a true difference of 59 mL between the treatments. If the withdrawal rate at 24 weeks exceeds 25% overall, additional patients may be randomized to the study to compensate for the loss of data.

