9.4 Statistical Analyses

9.4.1 Efficacy Analyses

Efficacy analysis will primarily be performed on the mITT population. The primary endpoint and key secondary endpoints will also be evaluated using the PP population as a sensitivity analysis. Impact of imputations and various baseline characteristics will also be checked.

The primary endpoint, change from baseline in FEV₁ AUC_{0-12h} at Week 12, will be compared between treatments using an analysis of covariance (ANCOVA) model adjusting for treatment, region, background medication strata, and smoking status as factors and baseline FEV₁ as covariate. The estimated treatment difference with 95% confidence interval and associated (two-sided) p-value will be presented. Missing data will be imputed to get as close to the mITT population as possible. Primarily imputation will be based on data collected at visits performed after treatment withdrawal or at early termination visits even if outside visit window. When no such data is available, imputation will primarily be done using multiple imputation based on baseline characteristics and secondarily, as a sensitivity analysis, by the average change in the opposite treatment group as randomized to as a worst-case scenario. Further details on the handling of missing data will be given in the Statistical Analysis Plan.

Key secondary endpoints, FEV₁ AUC_{0-4h}, peak FEV₁, morning trough FEV₁, SGRQ total score and weekly mean E-RS total score, and other continuous secondary or exploratory endpoints will be assessed repeatedly during the study and the change from baseline to pre-specified time point of evaluation will be compared by similar ANCOVA models adjusting for treatment, region, background medication strata and smoking status as factors and baseline as covariate. Data collected at visits performed after treatment withdrawal or at early termination visits will be used in the analyses. Remaining missing data will primarily be imputed using multiple imputation based on baseline characteristics and data collected at post-randomization visits. Since assessed repeatedly, in contrast to primary endpoint, these data will also be analyzed for sensitivity by mixed model repeated measures models with treatment, visit and treatment by visit interaction as factors, baseline as covariate, subject as random factor and covariance structure by visit.

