9.4.4 Missing Data

All data collected after treatment withdrawal will be used in the analyses. Patients withdrawn from study will perform an End-of-Study visit after decision to withdraw the patient has been made. Data collected at such visits will be used for analysis even if outside the visit window for the endpoint. Remaining missing data will primarily be imputed using multiple imputation based on baseline characteristics and data collected at post-randomization visits. In addition, a worst-case scenario using the average change in the opposite treatment group will be used for imputation as a sensitivity analysis. For the responder analysis of SGRQ, patients with no available data for imputation will be considered non-responders as a sensitivity analysis. In exacerbation analyses, patients are included with data collected up to last day in the treatment period/period of recording following treatment withdrawal.

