7.2. MULTICENTER STUDIES

This study will be conducted by multiple investigators at multiple centers internationally. Randomization to treatment arms is not stratified by country/ center.

When specified, statistical analysis will be adjusted for geographic region. Geographic region will be categorized as shown in Table 3:.

Table 3: Geographic Regions

Geographic Region	Country
Europe	Belgium, Bulgaria, Denmark, Hungary, Poland, Slovakia, Estonia, Spain
North America	United States, Canada

7.3.MISSING DATA

Missing safety data will not be imputed.

All data collected during the scheduled visits for patients on-treatment and off-treatment, for patients with treatment withdrawal, as well as the end-of-study visits for patients withdrawing from the study will be used for analysis performed on the mITT and that the remaining missing values will be handled as described in sections 16.1.2, 16.2.2 and 16.3.2 of the SAP.

7.4.MULTIPLE COMPARISONS/ MULTIPLICITY

To address multiplicity in the analysis of the endpoints, statistical testing of the primary endpoint and key secondary endpoints will be done in the hierarchical order (listed below). Initially the primary endpoint will be checked to see if comparison between active treatment and placebo is statistically significant. If yes, the first key secondary endpoint will be evaluated. If yes, the next key secondary endpoint will be evaluated. This process will continue until either all endpoints are evaluated, or if one of the endpoints' comparison is not significant.

Order of the endpoints that will be used for the hierarchical testing:

1. Change from baseline FEV₁ to FEV₁ AUC_{0-12h} at Week 12
2. Change from baseline FEV₁ to peak FEV₁ at Week 12
3. Change from baseline (i.e. mean over the last 7 days of run-in) to the mean weekly value at Week 24 in COPD symptoms, as measured by daily diary (E-RSTM:COPD)
4. Change from baseline in the SGRQ total score at Week 24
5. Change from baseline FEV₁ to morning trough FEV₁ at Week 12
6. Change from baseline FEV₁ to average FEV₁ AUC_{0-4h} at Week 12
7. Proportion of SGRQ responders at Week 24

7.5.EXAMINATION OF SUBGROUPS

Subgroup analyses will be conducted as stated in the efficacy analysis and disposition sections. Primary aim for the subgroup analysis is to check whether there are differences in treatment effect between strata or subgroups, which will be tested through interaction. For each analysis

by subgroup the results will be summarized as follows:

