16.1.2. MISSING DATA METHODS FOR PRIMARY EFFICACY VARIABLE

The main analysis for the primary endpoint will include estimates from missing data imputation described below. This is done to investigate the influence of missing data due to drop-outs. Only patients with non-missing baseline will be included in the analysis.

The primary analysis will be analyzed using MI based on the missing data assumption Missing at Random (MAR). This process will follow four steps:

1. Partially impute the data for a monotone missing pattern with 100 as a number of imputations and “20905” as seed number. Employ the Markov Chain Monte Carlo (MCMC) method with treatment, region, background medication strata, smoking strata, baseline FEV₁ and average FEV₁ AUC_{0-12h} at Week 12.

The following SAS codes will be used:

```
proc mi data=<data1> out=<data2> nimpute=100 seed=20905;
```

```
var <treatment> <region> <BackgroundMedStrata> <SmokingStrata>
  <baseline> <visits>;
mcmc impute=monotone chain=multiple;
run;
```

2. Impute the monotone data using a regression imputation model. Apply by imputation using seed number “20905” with treatment, region, background medication strata, smoking strata, baseline FEV₁ and average FEV₁ AUC_{0-12h} at Week 12.

The following SAS codes will be used:

```
proc mi data=<data2> out=<dataout> nimpute=1 seed=20905;
  by _imputation_;
  class <treatment> <region> <BackgroundMedStrata>
    <SmokingStrata>;
  var <treatment> <region> <BackgroundMedStrata>
    <SmokingStrata> <baseline> <visits>;
  monotone regression;
run;
```

3. Each multiple imputed dataset in Step 2 will be analyzed separately, as described in section 16.1.3 of the SAP.
4. The estimates (LS means, SE, CI, and p-value) from the model analysis in Step 3 will be combined using Rubin’s combination rules for statistical inference.

Sensitivity analysis will be done using:

- Average imputation will be based on data collected on treatment at required visit, or at early termination visit. This will be done on patient level. If there is no such data available, impute with average change from baseline for the particular visit in the opposite randomized treatment group.

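### As worded, the SAP's average-imputation sensitivity analysis leaves out off-treatment values measured at the required visit, contrary to the protocol, the treatment-policy estimand and SAP 7.3

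*SAP*

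**What the plan says.** **SAP 16.1.2** defines the average-imputation sensitivity analysis for the primary endpoint: "Average imputation will be based on data collected on treatment at required visit, or at early termination visit". Where a patient has nothing of that kind, the mean change from baseline at that visit in the other randomized arm is used. SAP 16.2.2.4 applies the same method to the key secondary endpoints.

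**Protocol 9.4.1** describes the data that come before any statistical imputation: "Primarily imputation will be based on data collected at visits performed after treatment withdrawal or at early termination visits even if outside visit window". The opposite-arm average is a worst-case sensitivity method, used only when no such data exist.

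**Protocol 9.4.4** is general: "All data collected after treatment withdrawal will be used in the analyses". Imputation is for what remains missing.

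**SAP Table 1** sets a treatment-policy strategy for stopping treatment. **SAP 7.3** agrees with it for analyses on the mITT: "All data collected during the scheduled visits for patients on-treatment and off-treatment" are to be used, together with end-of-study visits, and 16.1.2 is to deal with the values still missing after that.

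**SAP 3.3**, the list of changes from the protocol, does not mention an on-treatment restriction. It does list another change to a missing-data sensitivity analysis, the removal of non-responder imputation for SGRQ.

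**The concern.** The sentence in 16.1.2 names two acceptable sources: an on-treatment value at the required visit, and an early-termination value. An off-treatment value at the required visit is neither. Such values are expected, because Protocol 7.2 wants patients who stop drug to keep attending scheduled visits, and the reduced-assessment option in 7.2.1 keeps spirometry.

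The phrase cannot be dismissed as loose drafting. SAP 16.1.4 defines one observed-data analysis that takes data whether or not the patient is on treatment, and another restricted to patients still on randomized treatment. The SAP therefore draws this distinction on purpose elsewhere, and a programmer could reasonably apply 16.1.2 as written.

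A sensitivity analysis of missing data should hold the estimand fixed and vary only the assumption about unobserved values. Under the literal rule, this one also discards some observed values that the treatment-policy estimand needs. If its result differed from the primary analysis, part of the difference could come from the discarded data.

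**Working it through.** **The plan's own figure.** Protocol 9.2 gives these inputs: "The standard deviation for the change in FEV₁ AUC_{0-12h} is estimated to be 250 mL"; "With a 2-sided test at a 5% significance level"; "500 vs. 300 evaluable patients in the two groups, there will be an 90% power to detect a true difference of 59 mL". The standard error of the difference is 250·√(1/500 + 1/300) = 18.3 mL. Power is Φ(59/18.26 − 1.96) = Φ(1.27) = 89.8%, which reproduces the stated 90%. The point does not dispute this figure; 59 mL and 250 mL serve only as a scale.

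**Who is affected under the literal rule.** The table covers patients who stopped drug before Week 12.

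| Data available | Protocol 9.4.1/9.4.4 and SAP 7.3 | SAP 16.1.2, literal |
|---|---|---|
| Off-drug Week 12 value, no usable early-termination value | Week 12 value used | Opposite-arm mean |
| Off-drug Week 12 value and early-termination value | Week 12 value is available for use | Early-termination value used |
| Early-termination value only | Early-termination value used | Early-termination value used |
| Neither | Opposite-arm mean (as sensitivity) | Opposite-arm mean |

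Only the first two rows differ. For the second row, SAP 6.4 lets an end-of-study visit fill only a visit that is missing or has a missing result. That is the reverse of the order 16.1.2 implies.

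**Size for the first row.** Let d be the on-drug difference, f the share per arm in that row (taken as equal in both arms), and r the share of the effect kept off drug. Set the placebo mean to 0.

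- Measured values kept: active (1−f)d + f·r·d, placebo 0. Difference d(1 − f + f·r).
- Literal rule: active (1−f)d + f·0, placebo f·d. Difference d(1 − 2f).
- Gap: d·f·(1+r).

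At r = 0 the whole gap comes from off-drug placebo values being replaced by the ensifentrine mean.

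With d = 59 mL:

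| f | Kept, r = 0 | Literal rule | Gap, r = 0 | Gap, r = 0.5 | Power kept vs literal (r = 0, SD 250) |
|---|---|---|---|---|---|
| 1% | 58.4 | 57.8 | 0.6 | 0.9 | 89.2% vs 88.6% |
| 2% | 57.8 | 56.6 | 1.2 | 1.8 | 88.6% vs 87.3% |
| 5% | 56.1 | 53.1 | 3.0 | 4.4 | 86.7% vs 82.9% |
| 10% | 53.1 | 47.2 | 5.9 | 8.9 | 82.9% vs 73.4% |
| 20% | 47.2 | 35.4 | 11.8 | 17.7 | 73.4% vs 49.2% |

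Estimates and gaps are in mL. Imputing a constant also shrinks the apparent SD, which offsets part of the loss of power: with that allowed for, the literal-rule power is 84.6% at f = 5% and 77.6% at f = 10%.

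The formula ignores patients with no data at all, who are treated alike under both rules. Adding 5% of them per arm at f = 5% and r = 0 gives:

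- Literal rule: 0.9·59 − 0.1·59 = 47.2 mL.
- Values kept: 53.1 − 0.05·(53.1/0.95) = 50.3 mL.

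The gap is 3.1 mL instead of 3.0, so the simplification matters little.

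**The case against.** The strongest reply is that 16.1.2 must be read with SAP 7.3. Section 7.3 first uses all on- and off-treatment visit data and sends only the remaining missing values to 16.1.2. That section is about missing data, and it nowhere says that a measured value is to be replaced. On that reading the SAP matches the protocol and 3.3 has nothing to declare. This is a fair account of what may have been intended, but it does not remove the stated rule. It shows that 7.3 and 16.1.2 conflict, and 16.1.4 shows that the SAP can use on-treatment status as a deliberate restriction.

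Other parts of the reply stand and limit the point.

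- A reader might infer that every patient who stopped drug and attended Week 12 loses that value to the opposite-arm mean. The documents do not support this. Early-termination values are accepted without having to be on drug, and Protocol 7.1 asks most patients who stop drug to complete the withdrawal assessments. Off-drug spirometry at that visit is, however, optional (Protocol 7.3.1.1). Two of the three reduced follow-up options (7.2.2 and 7.2.3) include no Week 12 spirometry, so those patients have no Week 12 measurement to lose.
- A reader might infer that robustness to missing data can no longer be judged. It can. The tipping-point analysis in 16.1.2 shifts imputed values only, and the two observed-data analyses in 16.1.4 can be compared to show the effect of off-drug data.
- The size is modest. At f = 5% the gap of 3.0 to 4.4 mL is about 0.2 standard errors (3.0/18.3 = 0.16; 4.4/18.3 = 0.24).

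**Conclusion.** The point holds as a defect in the wording of one sensitivity analysis. SAP 16.1.2 conflicts with Protocol 9.4.1 and 9.4.4, with the treatment-policy estimand and with SAP 7.3. The departure is undeclared, and it extends to the key secondary endpoints.

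It does not reach the primary result: the primary multiple-imputation analysis keeps off-treatment data under SAP 7.3. Nor could the rule flatter the drug if the drug works, because the distortion then runs against ensifentrine. The risk is a false sign of fragility in an analysis the protocol already calls a worst case.

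For the primary endpoint the excess harshness is about 59·f·(1+r) mL: under 1 mL if 1% of each arm is affected, 3.0 to 4.4 mL at 5%, and 5.9 to 8.9 mL at 10%, for r from 0 to 0.5. These sizes rest on an assumed f (equal in both arms), an assumed r, and the design difference of 59 mL. The documents give neither f nor r, so the number of patients affected cannot be derived. Patients who have both values are not covered by the formula. The mL figures do not carry over to the symptom and quality-of-life endpoints.

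**What to change.** Reword the average-imputation sentence in SAP 16.1.2 to:

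> *All observed values at the required visit, on or off treatment, are kept; early-termination values are used where the required visit is missing; only values still missing are imputed with the average change in the opposite randomized group.*

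SAP 16.2.2.4 then inherits the corrected rule by its cross-reference. If an on-treatment version is really wanted, keep it under its own name as a separate supplementary analysis and list it in SAP 3.3.

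The cost is one SAP sentence and the matching program logic. No extra data are needed, and the sample-size figure does not change. If the drug works, the stress test becomes slightly less extreme. No information is lost, because SAP 16.1.4 already includes an on-treatment observed-data analysis.

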16.1.3. PRIMARY ANALYSIS OF PRIMARY EFFICACY VARIABLE

The primary objective of this study is to test the hypothesis that there is a difference between ensifentrine in comparison with placebo.

The change from baseline FEV₁ to average FEV₁ AUC_{0-12h} will be compared between ensifentrine and placebo using ANCOVA with fixed effects for treatment, region, background medication strata and smoking strata and baseline FEV₁ as covariate. Missing data will be imputed using imputation described in section 16.1.2 of the SAP. The estimated treatment difference will be presented with 95% CI and associated p-value. Furthermore, SD will be presented for the treatment difference to check the sample size with 90% power. Summary statistics will be performed on the imputed values.

Model assumptions will be tested as per the following rules on the blinded data, before the DBL.

1. Residual vs Predicted plots will be created to check residuals are uncorrelated and normally distributed.
2. Normality of the data will be checked using Kolmogorov-Smirnov normality test.

If any of the checks specified above fail the test, then alternative approaches will be discussed, including different ways of transposing data. The SAP will be updated to reflect any changes prior to DBL.

Only spirometry measurements with best test review (BTR) grades “Acceptable” and “Borderline Acceptable” are used in the analysis and baseline calculations.

16.1.4. SENSITIVITY ANALYSIS OF PRIMARY EFFICACY VARIABLE

The primary endpoint will be presented for the following:

- Subgroup analysis will be performed by subgroups, including data imputation described in sections 7.5 and 16.1.2 of the SAP, respectively.
- Observed data analysis will be performed by the following subgroups:
 - Analysis with no data imputation, including all patients with data collected, on treatment or not, and at required timepoint or at EOS visit (excluding patients with missing data).
 - Analysis with no data imputation, including only patients with data collected at the

required visit while still on randomized treatment at scheduled visit, or at end of study visit within the visit window.

- Average imputation, as described in section 16.1.2 of the SAP.
- Analysis with tipping point approach, as described in section 16.1.2 of the SAP.
- Analysis with multiple imputation, as described in sections 16.1.2 and 16.1.3 of the SAP, based on PP population.

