4.2. INTERIM ANALYSIS

There is no interim analysis planned for this study, however additional patients may be randomized if:

- the SD has increased significantly from the estimated 250 mL, as per sponsor discretion, and/or
- the withdrawal rate at 24 weeks exceeds 25% overall, and the percentage of patients with missing FEV₁ over 12 hours at Week 12 in mITT (modified Intent-to-Treat) population exceeds 20% overall.

Note: As part of the primary endpoint analysis, SD of the treatment difference is calculated to check the sample size with 90% power.

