- Complete data with added fixed effect to the model: subgroup*treatment.
- Data split by subgroup using the main model.

The following subgroups will be assessed and described within the analysis sections 16.1.4 and 16.2.4 of the SAP.

- Gender at birth:
 - Female
 - Male
- Age-class (years):
 - <65
 - ≥65
- Region
 - Europe
 - North America
- Actual Background medication strata
 - Yes
 - No
- Actual Smoking strata
 - Current
 - Former
- Actual ICS use
 - Yes
 - No
- Known chronic bronchitis
 - Yes
 - No
- FEV₁ reversibility at screening (≥12% and ≥200mL increase in FEV₁)
 - Yes
 - No
- COPD severity
 - Moderate (50% ≤ post-bronchodilator FEV₁ at screening < 80% predicted)
 - Severe (30% ≤ post-bronchodilator FEV₁ at screening <50% predicted)
 - Very severe (post-bronchodilator FEV₁ at screening <30% predicted)

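### The primary endpoint's subgroup interaction tests use imputations that assume one common treatment effect, which biases the interaction and usually costs power

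*SAP*

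**What the plan says.** SAP 7.5 gives the main purpose of the subgroup analyses as looking for "differences in treatment effect between strata or subgroups, which will be tested through interaction". Two analyses are planned for each factor. One is a model on all patients: "Complete data with added fixed effect to the model: subgroup*treatment". The other fits the main model separately within each subgroup level. Nine factors are listed: gender, age class, region, background therapy, smoking, ICS use, chronic bronchitis, FEV1 reversibility and COPD severity.

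For the primary endpoint, SAP 16.1.4 states: "Subgroup analysis will be performed by subgroups, including data imputation described in sections 7.5 and 16.1.2 of the SAP, respectively". Section 7.5 contains no imputation method, so 16.1.2 governs. Its first step reads "Employ the Markov Chain Monte Carlo (MCMC) method with treatment, region, background medication strata, smoking strata", followed by baseline FEV1 and the Week 12 average FEV1 AUC0-12h. The second step, a regression imputation, uses the same variables. The PROC MI code for both steps lists main effects only. Region, background therapy and smoking are present without a product term, and the other six factors are absent. Neither section asks for the imputation to be repeated with a subgroup term. The observed-data items in 16.1.4 define which data are used, so no unimputed interaction analysis is clearly planned.

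**The concern.** The interaction model estimates a quantity that the imputation model has fixed at zero. Each imputed patient receives the common treatment effect, whatever the subgroup. The combined estimate therefore mixes the observed interaction with an imputed interaction of zero, in proportion to the amount missing. Rubin's rules do not correct this, because the between-imputation variance is added as if the imputation model were compatible with the analysis model.

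At stake is the evidence on consistency of effect. A non-significant interaction would partly reflect how the missing values were filled in. If the imputed data sets are split after imputation, the subgroup-specific estimates are affected too.

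**Working it through.** **Inputs from the documents.** Protocol 9.2: "With a 2-sided test at a 5% significance level and 500 vs. 300 evaluable patients in the two groups"; the SD of the change in FEV1 AUC0-12h "is estimated to be 250 mL". SAP 16.1.2: 100 imputations, missing at random. SAP 4.2 gives only a trigger for adding patients, part of which is that missing 12-hour FEV1 at Week 12 in the mITT "population exceeds 20% overall".

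**Assumptions.** The missing fraction f runs from 5% to 20%. The true interaction is the one with 80% power if nothing were missing.

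**The plan's own figure.** SE = 250 × √(1/500 + 1/300) = 18.26 mL. Power = Φ(59/18.26 − 1.96) = Φ(1.27) = 0.898, which reproduces "90% power to detect a true difference of 59 mL between the treatments".

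**Interaction with complete data.**
- 50% subgroup (cells 250, 250, 150, 150): SE = 250 × √(2/250 + 2/150) = 36.51 mL. The interaction with 80% power is 36.51 × (1.960 + 0.842) = 102.3 mL.
- 20% subgroup (cells 100, 400, 60, 240): SE = 45.64 mL, giving 127.9 mL.

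**Effect of the imputation, equal missingness f in every cell.** Let V be the complete-data variance and δ the true interaction. In large samples:
- expected estimate = (1 − f)δ
- Rubin variance ≈ (1 + f)V
- actual variance ≈ (1 − f)V
- power ≈ Φ{[(1 − f)δ/√((1 + f)V) − 1.96] / √((1 − f)/(1 + f))}

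At f = 0.20 the estimate is 0.8 × 102.3 = 81.8 mL. The Rubin SE is 36.51 × √1.2 = 40.0 mL, against an actual SD of 36.51 × √0.8 = 32.7 mL. Power is Φ[(2.046 − 1.960)/0.816] = 0.54. The type I error is 2 × [1 − Φ(1.960/0.816)] = 1.6%.

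**Simulation.** 2,500 trials per setting (3,000 for type I error), 100 imputations, regression imputation on the SAP's variables, ANCOVA with the interaction, and Rubin's rules. Patients without a baseline are excluded, so only the Week 12 value can be missing and the regression step does the work. The table is for a 50% subgroup and a true interaction of 102.3 mL, with the factor present as a main effect in the imputation. The fix adds subgroup and subgroup-by-treatment to the imputation.

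| Missing | Formula estimate, mL | Simulated estimate, plan / fix, mL | Formula power, plan | Simulated power, plan / fix | Type I error, plan: formula / simulated | Type I error, fix |
|---|---|---|---|---|---|---|
| 5% | 97.2 | 97.7 / 102.9 | 75% | 76% / 78% | 3.9% / not run | not run |
| 10% | 92.1 | 92.2 / 102.5 | 69% | 69% / 77% | 3.0% / 2.7% | 4.4% |
| 20% | 81.8 | 82.2 / 103.0 | 54% | 54% / 70% | 1.6% / 1.4% | 4.9% |

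With the factor absent from the imputation model, the plan gives 91.4 mL and 67% power (fix 74%) at 10% missing, and 81.4 mL and 53% (fix 70%) at 20%. For a 20% subgroup with a true 127.9 mL and 20% missing, it gives 103.4 mL and 54% (fix 72%).

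**Unequal missingness, omitted factor.** Take 10% missing on ensifentrine, 20% on placebo, and an assumed 100 mL effect of the subgroup itself on the change. The imputed values carry no subgroup difference, so the subgroup contrast is diluted by a different amount in each arm:
- True interaction 0: 0.9 × 100 − 0.8 × 100 = +10 mL. Simulated: +11.3 mL under the plan, +1.5 mL after the fix. The observed-data analysis of the same trials also gives +1.5 mL, so that residue is simulation noise.
- True interaction 102.3 mL: 0.9 × 202.3 − 0.8 × 100 = 102.1 mL. Simulated: 102.7 mL. The shrinkage is cancelled.

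**The case against.** **Section 16.1.4 cites a method; it does not say that pooled imputed data sets are carried over.** One could split first and then impute within each level. That reading is open for the split-by-subgroup estimates and would rescue them. It does not rescue the interaction test, which is fitted to all patients and for which nothing adds an interaction to the imputation.

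**Missingness may be low.** This stands. SAP 7.3 uses off-treatment and end-of-study data before imputing, 6.4 maps early 12-hour spirometry to Week 12, and 16.1.1.1 accepts an AUC observed only to 8 hours. The 20% in SAP 4.2 is part of a trigger and not a forecast. The 25% withdrawal figure refers to Week 24, so it is no basis for a Week 12 missing rate.

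**The error is conservative and outside the alpha hierarchy.** This is largely right under equal missingness. At 20% missing and 102.3 mL, the bias is −20.5 mL and the interval half-width is 1.96 × 40.0 = 78.4 mL. Coverage is about Φ[(78.4 − 20.5)/32.7] = 96%. But a test that rejects 1.4% of the time at a nominal 5% is poorly suited to finding differences, which is its stated purpose.

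**The 7.5 wording.** A reader might infer that adding only the product term, coded literally for a factor with no main effect in the model, would also test the subgroup main effect. Section 7.5 says that differences in treatment effect are what is tested, so that coding would contradict the stated aim. It deserves a wording note, not a finding.

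**Conclusion.** The concern holds for the primary endpoint's interaction tests. Under equal missingness across cells, the interaction is attenuated by about the missing fraction and the SE is too large. The power loss is about 3 points at 5% missing (75.6% against 78.3% before rounding), 8 at 10% and 16 at 20%. This rests on a true interaction of 102 mL, a 50% subgroup and an SD of 250 mL. The interaction size and the missing rates are assumptions, and the trial is not sized for interactions.

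Three stronger readings are tempting but not supported:
- That the tests always lean towards no difference. For the six omitted factors, arm-dependent missingness together with a subgroup effect on the outcome can create an apparent interaction or cancel the shrinkage.
- That the trial's main conclusion is at risk. The overall primary comparison and the hierarchy in SAP 7.4 do not use these analyses.
- That the key secondary endpoints suffer equally. Their imputation (SAP 16.2.2.1) includes all scheduled visits, so the shrinkage is probably smaller. It was not quantified.

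**What to change.** In SAP 16.1.4, and in 16.2.4 for consistency, state that each subgroup analysis has its own imputation, with subgroup and subgroup-by-treatment added to both PROC MI steps. The first step has no CLASS statement, so the product must be entered there as a computed variable. Imputing separately by treatment arm with the subgroup as a covariate is an alternative. Report the observed-data interaction alongside. In the simulations the two agreed closely.

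As a wording note, write the 7.5 interaction model as main model + subgroup + subgroup-by-treatment, and test only the interaction.

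The cost is SAP text and one extra imputation run per factor and endpoint. The very severe COPD category (below 30% predicted) should be nearly empty, because protocol inclusion criterion 7 requires at least 30%. It must be merged with severe for imputation.
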